7.7.2. Plasma Pharmacokinetic Parameters for Encorafenib, LHY746, and Binimetinib

PK parameters for participants in the PK set will be determined for encorafenib, its metabolite (LHY746), and binimetinib, when possible and appropriate. Only participants assigned to the serial PK blood sampling schedule will be included in the PK parameter assessment.

The individual plasma concentration-time data for each analyte will be evaluated with noncompartmental analysis (NCA) using Phoenix WinNonlin®, Version 8.0 or higher. Actual blood collection times and doses will be used for PK calculations. If actual times are not recorded/available, nominal times will be used. All BLQ values before the observed maximum plasma concentration (C_{max}) will be set to 0; all BLQ values after C_{max} or embedded between two measurable values will be considered as missing.

The PK parameters that will be calculated for encorafenib, its metabolite (LHY746), and binimetinib on C1D1 and C1D15 are defined in Table 9.

The AUC parameters will be calculated according to the linear-up log-down trapezoidal rule. Additional PK parameters may be calculated at the discretion of the pharmacokineticist.

All PK parameter values will be presented in data listings by analyte, cycle and study day. Each parameter will be summarized in tables by line of therapy (treatment naive, previously treated, and overall), analyte, cycle and study day using the following descriptive statistics: N, n, arithmetic mean, standard deviation, CV, geometric mean, geometric CV, minimum, median and maximum. Descriptive statistics for in-text summary tables will include geometric mean with geometric CV for AUC, C_{max} , and RAUC. For T_{max} values, median, minimum and maximum will be presented. Pharmacokinetic parameters will be excluded from the calculation of summary statistics if any of the above flags [a-c] apply.

Table 9. Definitions of Pharmacokinetic Parameters

PK Parameter	Definition
AUC_{0-6}	Area under the plasma concentration-time curve from zero to 6 hours
AUC_{last}	Area under the plasma concentration-time curve from zero to the last measurable time point
AUC_{tau}	Area under the plasma concentration-time curve over a dosing interval at steady-state (C1D15 only) To estimate AUC_{tau} , the concentration measured at predose on C1D15 will be imputed as the concentration at the end of the dosing interval (i.e., 12 or 24 hours, as appropriate) assuming steady-state has been attained
C_{max}	Observed maximum plasma concentration
C_{trough}	Trough (predose) concentration at steady state
T_{max}	Observed time of C_{max}
T_{last}	Observed time of last measured concentration

Table 9. Definitions of Pharmacokinetic Parameters

PK Parameter	Definition
MR _{C_{max}}	Ratio of C _{max} values of the metabolite compared to parent, corrected for molecular weight, for LHY746/ Encorafenib only
MR _{AUC_{last}}	Ratio of AUC _{last} values of the metabolite compared to parent, corrected for molecular weight, for LHY746/ Encorafenib only

7.7.3. Statistical Assessment of Accumulation

For statistical analysis of accumulation of encorafenib, its metabolite (LHY746), and binimetinib, the accumulation ratio will be estimated for serial PK sampling participants by making comparisons of AUC₀₋₆, AUC_{last} and C_{max} on C1D15 with corresponding estimates on C1D1; a mixed-effects model will be fitted to log-transformed AUC₀₋₆, AUC_{last} and C_{max} including day as a fixed effect and subject as a random effect. This model will be used to estimate the accumulation ratio (C1D15 / C1D1) with 90% CIs. The geometric least square means and ratio with 90% CIs will be tabulated.

7.7.4. Statistical Assessment of Cigarette Smoking on PK Exposure

The impact of cigarette smoking on encorafenib and binimetinib metabolism will be explored. Smoking history collected will be used to calculate the median number of cigarettes smoked by the participant population per day, and the exposure of encorafenib, its metabolite (LHY746), and binimetinib (AUC₀₋₆ and C_{max}) will be summarized with participants stratified based on this: zero, less than the median, or, greater than or equal to the median number of cigarettes, using the following descriptive statistics: N, n, arithmetic mean, standard deviation, CV, geometric mean, geometric CV, minimum, median and maximum. If the median is zero, the participants will be stratified by zero and non-zero cigarettes.

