| Section 7.8 Pharmacokinetics Section 7.8 Table 12 Serial Pharmacokinetic Blood Sample Timing in patients Enrolled under Protocol Versions 0 through 3 Section 7.8 Table 13 Pharmacokinetic Blood Sample Timing in patients enrolled under protocol version 4 or later | Updated PK collection schedule; clarified Table 12 and added Table 13 to reflect new schedules. | Approximately 50 patients enrolled under the Protocol Version 3 have provided serial PK samples, which are sufficient to characterize PK in this population. To reduce patient burden, only predose PK samples will be collected from future patients for exposure-response analysis. FDA agreed on the changes of PK collection. |
| Section 7.10.2 Circulating Serum Biomarker Analysis | Added section for additional samples collected. | To monitor proteomic correlates of response and resistance to therapy. |
| Section 8 Statistical Considerations | Revised to update changes to statistical analyses due to sample size updates and to support registrational status of study. | Following consultation with the FDA, the design of the study has been revised to allow for registration of either or both a treatment naïve population and a previously treated population |
| Section 8.1 Statistical Hypotheses | Updated to reflect new calculations for the 2 subgroups. | Following consultation with the FDA, the design of the study has been revised to allow for regulatory approval of either or both a treatment naïve population and a previously treated population. |
| Section 8.2 Sample Size Determination | Updated to reflect the sample size for each subgroup. | Following consultation with the FDA, the design of the study has been revised to allow for regulatory approval of either or both a treatment naïve population and a previously treated population. |
| Appendix 7 Snellen Equivalence (Visual Acuity Conversion Chart) | Included conversion chart of visual acuity reading. | To assist in the consistent conversion of values, the conversion chart has been included. |

Version 3 (25 August 2020) The primary purpose of this amendment is to increase the sample size to support a potential registrational status of the study, and to provide clarification on acceptable methods for BRAF mutation status confirmation. Country specific changes per Korean Amendment 2.1 and 2.2 have been incorporated. This amendment is considered to be substantial based on the criteria set forth in Article 10(a) of Directive

Version 5

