7.4.1. Demographics and Pretreatment Characteristics

Demographic and other pretreatment characteristics including age, gender, race, ethnicity, height, weight, and ECOG performance status at baseline will be summarized.

In addition, the tobacco use status collected on the Tobacco Use eCRF page will be summarized (current smoker, former smoker, and non-smoker), considering cigarette, cigar, pipe, e-cigarette, and vape.

A demographics listing by participant will be presented.

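### The smoking cut-point in SAP 7.7.4 is a median that includes zero-cigarette participants, so the two smoker strata are unbalanced, and severely so as the share of zeros nears 50%

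*SAP*

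**What the plan says.** SAP 7.7.4 gives its aim as follows: "The impact of cigarette smoking on encorafenib and binimetinib metabolism will be explored". The cut-point is set in these words: "Smoking history collected will be used to calculate the median number of cigarettes smoked by the participant population per day". AUC0-6 and Cmax are then to be summarised in three strata: "zero, less than the median, or, greater than or equal to the median number of cigarettes". A fallback follows: "If the median is zero, the participants will be stratified by zero and non-zero cigarettes".

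The parameters being summarised exist for only part of the trial. SAP 7.7.2 says: "Only participants assigned to the serial PK blood sampling schedule will be included in the PK parameter assessment". The one indication of how many that is comes from a rationale entry in Protocol Appendix 9: "Approximately 50 patients enrolled under the Protocol Version 3 have provided serial PK samples".

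SAP 7.4.1 classifies tobacco use as "current smoker, former smoker, and non-smoker". Neither document gives the proportions, and SAP 7.7.4 does not say whether a former smoker counts as zero or by past consumption.

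**The concern.** A median among people who smoke at least one cigarette a day could never be zero. The fallback therefore makes sense only if zero-cigarette participants are in the calculation. They pull the cut-point down and are then set aside as a separate stratum, so what remains is not a median split of smokers. The position of the cut depends on how many non-smokers were enrolled as well as on how much the smokers smoke.

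What is at stake is the comparison of lighter with heavier smokers, which is the reason for having three strata rather than two. A thin lower stratum gives an imprecise summary. With a single participant, the standard deviation, CV and geometric CV that the SAP asks for cannot be calculated.

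**Working it through.** The plan states no figure for the strata, so there is none to reproduce. The sizes follow from the definition of a median.

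**Inputs**
- The median is taken over the participant population, zeros included (SAP 7.7.4 and its fallback).
- N is about 50 with serial PK (Protocol Appendix 9). This is used only to set the scale.
- p0, the share at zero cigarettes, is not in the documents. It is an assumption and is varied below.
- Two further assumptions: no ties among smokers, and the median and the strata use the same participants.

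**Formulas for p0 below 0.5**
- Low stratum, share of all participants: 0.5 − p0
- Top stratum, share of all participants: 0.5
- Low stratum, share of smokers: (0.5 − p0)/(1 − p0)
- Top stratum, share of smokers: 0.5/(1 − p0)

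**Stratum sizes at N = 50**

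| p0 | SAP rule: zero/low/high | Low, % of smokers | Smokers-only median: low/high |
|---|---|---|---|
| 10% | 5/20/25 | 44% | 22/23 |
| 20% | 10/15/25 | 38% | 20/20 |
| 30% | 15/10/25 | 29% | 17/18 |
| 40% | 20/5/25 | 17% | 15/15 |
| 44% | 22/3/25 | 11% | 14/14 |
| 48% | 24/1/25 | 4% | 13/13 |
| 50% | 25/0/25 | 0% | 12/13 |
| 60% | 30 zero, 20 non-zero (fallback) | no split | 10/10 |

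At exactly 50% with an even N, the usual median averages zero and the smallest non-zero count. It is above zero, so the fallback is not triggered and the low stratum is empty.

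**When the imbalance becomes extreme.** The top stratum holds at least 80% of smokers when p0 ≥ 1 − 0.5/0.8 = 37.5%. It holds at least 90% when p0 ≥ 1 − 0.5/0.9 = 44.4%.

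**Precision of the light-versus-heavy contrast.** With equal variance, the standard error is proportional to √(1/n_low + 1/n_high).
- p0 = 30%: √(1/10 + 1/25) = 0.374 under the SAP rule; √(2/17.5) = 0.338 under a smokers-only median. Ratio 1.1.
- p0 = 40%: √(1/5 + 1/25) = 0.490; √(2/15) = 0.365. Ratio 1.3.
- p0 = 45% (expected sizes 2.5 and 25, against 13.75 each): √(1/2.5 + 1/25) = 0.663; √(2/13.75) = 0.381. Ratio 1.7.

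**Effect of ties, as an illustration only.** Suppose smokers report 5, 10, 20, 30 or 40 a day in proportions of 15, 30, 40, 10 and 5%. The SAP rule then gives low/high of 6/34, 5/30 and 4/26 at p0 = 20, 30 and 40%. A smokers-only median gives 18/22, 16/19 and 13/17. Ties can thin the low stratum sooner under the SAP rule, and they leave a mild imbalance under the alternative.

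**The case against.** A reader might infer that the low stratum will be nearly empty and that the top one will hold almost every smoker. The documents do not support that. They report no smoking distribution, and without ties the description fits only p0 of about 44% to 50%. At 10% to 30% the low stratum still holds 44% to 29% of smokers. How former smokers are counted could move p0 a long way in either direction.

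A reader might also infer that the table cannot show an effect of smoking at all. That does not follow either. The zero stratum is the same wherever the cut falls, so non-smokers remain separate from smokers at every p0, and individual PK parameters are listed under SAP 7.7.2.

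Four further objections deserve an answer.
- Pooling all smokers when the median is zero is a written rule, not an oversight. That is correct, and pooling is sensible when smokers are few. But the rule is triggered by a majority at zero, not by a small number of smokers: at p0 = 60% there are 20 smokers of 50, enough for 10/10.
- A smokers-only median costs precision in the top stratum. It does: going from 25 to 17.5 or 15 raises that stratum's standard error by √(25/17.5) = 1.20 or √(25/15) = 1.29 at p0 = 30% or 40%. The contrast between the strata still gains.
- The sizes assume one population for the median and the strata. If the median is taken over all participants but PK parameters exist only for the serial group, the shares need not hold exactly in that group. SAP 7.7.2 also excludes flagged values, so 50 is not an analysis count. Both points stand as limits on the figures.
- The table is exploratory and has no test, interval or decision rule. This stands and sets the weight of the point.

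**Conclusion.** The point holds as a cheap improvement of low severity. As written, the SAP lets zero-cigarette participants set a cut-point meant to separate lighter from heavier smokers. Whenever zeros exist, the smoker strata are then unbalanced in the direction of a smaller low stratum. The imbalance is mild at p0 = 10%, clear at 30% and severe close to 50%. Above 50% the light/heavy comparison is dropped by rule.

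The counts and precision ratios rest on an assumed p0, no ties, one common population of about 50, and equal variances. Only the direction of the imbalance follows from the SAP text itself. Nothing here bears on ORR or on any other efficacy or safety conclusion.

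**What to change.** In SAP 7.7.4, define the cut-point as the median daily count among participants who have PK parameters and a non-zero cigarette count. Use the strata zero, below that median, and at or above it. Replace the zero-median fallback with zero versus non-zero, to apply only when there are too few smokers to split, and state that minimum number in advance. In the same edit, say whether former smokers count as zero or by past consumption, since this decides who falls in the zero stratum.

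The cost is a few sentences in the SAP and no new data. The top stratum will be smaller than under the present rule, and round-number reporting may still leave the two smoker strata somewhat unequal.

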7.7.5. Statistical Assessment of Line of Therapy on PK Exposure

The impact of line of therapy on PK exposures will be assessed between treatment-naïve and previously treated participants in the PK Analysis Set. Welch's 2-sided t-test for unequal variances will be used to assess the statistical significance of the differences for log-transformed PK parameter estimates (AUC₀₋₆, AUC_{tau}, and C_{max}), by analytes (encorafenib, LHY746, and binimetinib) on C1D1 and C1D15. The p-values will not be adjusted for multiplicity.

7.8. Interim Analysis

An interim analysis may be performed for treatment-naïve participants after about 90% [n=54] of the planned treatment-naïve participants [n=60] will be enrolled.

At the time of the interim analysis, if the posterior probability that the true ORR exceeds 39% is $\geq 80\%$, assuming a non-informative Beta (0.5,0.5) prior, then the data will be considered for discussions with regulatory authorities.

The Table 10 includes posterior probability for the expected number of participants and the observed responses at the first look.

Table 10. Posterior Probabilities

Enrolled Participants	Observed Responses	Posterior Probability for True ORR >39%
54	24	79.5
54	25	86.4
54	26	91.5
54	27	95.0
54	28	97.2
54	29	98.6

8. DATA AND ANALYSIS QUALITY ASSURANCE

This protocol was conducted under the sponsorship of Pfizer Inc. Personnel within Pfizer or CRO designee provided statistical and data management input for the design of the clinical trial protocol; data management, statistical analysis and generation of tables, listings and figures; and medical writing support for the clinical study report.

All parties mentioned above will work diligently and collaboratively to ensure that data collection and analysis for this study are of the highest quality. This will be accomplished through programmed edit checks, quality control processes, and clinical and statistical review of data displays. Quality and accuracy of statistical analyses will be verified through established statistical programming validation processes.

10. APPENDIX 1: EVALUATION OF RECIST (VERSION 1.1) TUMOR ASSESSMENT CRITERIA

The primary efficacy analysis is based on IRR assessment per RECIST 1.1. The secondary efficacy analysis is based on derived investigator assessment of tumor data and confirmation of response is required.

This section describes the rules used for derivation of tumor response and progression based on derived investigator assessment of tumor data for secondary efficacy analyses.

Uses “start date” to denote the date of first dose of study drug.

SPECIFICATIONS FOR PROGRAMMATIC DERIVATION OF TUMOR RESPONSE USING RECIST 1.1

The primary efficacy analysis will be based on IRR interpretation of tumor assessment scans from study sites, performed by Bioclinica. The details of this process are described in the study specific Bioclinica charter. Analyses based on IRR will use data as transferred from IRR:

- BOR (but not the target response, non-target response and time point response at each time point) will be derived using the rules presented in this appendix.
- Date of progressive disease (PD) and determination of event or censoring for progression-free survival will be derived, from the PD date reported by IRR, the dates of time point tumor assessments reported by IRR and accounting for anticancer therapy and other censoring rules.

A secondary efficacy analysis will be based on a programmatic approach to derive tumor response/progression, using RECIST 1.1 and the investigator tumor assessment data recorded on the target, non-target, and new lesion eCRFs, as described below.

The tumor response criteria are based on RECIST 1.1 (Eisenhauer EA, Therasse P, Bogaerts J, et al. New response evaluation criteria in solid tumours: Revised RECIST guideline [Version 1.1]. *Eur J Cancer*. 2009;45(2):228-47).

10.1. Study Specific Information

10.1.1. Interchangeable Methods of Tumor Assessment

If an inconsistency in imaging technique has occurred (e.g., a switch from CT to MRI or a switch from contrast to non-contrast), the independent radiologist will determine whether this change in technique affects tumor evaluation. Issues affecting response will be documented.

For the derivation of investigator’s assessment data CT/MRI/Spiral CT are considered interchangeable methods.

10.2. Lesion Evaluation at Assessment Times

10.2.1. Response Evaluation of Target Lesions

- Complete Response (CR) is defined by the disappearance of all non-lymph node target lesions (where all target lesions are recorded with a length of 0 mm on the “Target Lesions” eCRF). Any pathological lymph nodes (recorded as target lesion) must have reduction in short axis to <10 mm.
 - Note: the SOD may not be zero if lymph nodes are included as target lesions.
- Partial Response (PR) is defined by a 30% or more decrease in SOD of target lesions, taking as reference the baseline SOD.
- PD is defined by a 20% or more increase in the SOD of target lesions relative to nadir (smallest SOD considering baseline and all assessments prior to the time point under evaluation), with a minimum absolute increase of 5 mm relative to nadir.
 - Note: if only a subset of target lesions are assessed and the sum of the non-missing lesion diameters results in an increase above of at least 5 mm and at least 20% above the nadir, then the SOD will still be calculated and the progression criteria will have been otherwise met. If the sum of non-missing lesions does not indicate PD, then the SOD will be left as missing.
- Stable Disease (SD) is assigned when neither sufficient shrinkage to qualify for CR or PR, nor sufficient increase to qualify for PD is observed, taking as reference the nadir.
- No Target Lesion at Baseline (NB) is assigned if “No Target Lesion” is checked, on the “Lesion Assessment Y/N” eCRF at baseline.
 - Note: a protocol deviation should be reported.
- Not All Evaluated (NAE) is assigned if, in the absence of PD based on evaluated target lesions:
 - Any individual target lesion is evaluated as “Indeterminate” on the “Target Lesions” eCRF.
 - Inconsistent methods (unless considered “interchangeable”) are used for any target lesions after start date.
 - One or more target lesions are not assessed.
 - One or more target lesions were excised or irradiated and have not reappeared or increased.

Determination of target lesion response in case of reappearance of one or more target lesion(s) that have previously disappeared:

- If the previous target lesion response was CR, and a non-lymph node target lesion reappears, then the response is always PD.
- If the previous target lesion response was CR, and a lymph node target lesion reappears, then the response (whether CR or PD) is assessed based on PD criteria noted above. The response will be PD only if SOD criterion for PD is met and if the lymph node returns to pathologic size (≥ 10 mm) and meets the absolute requirement of 5 mm increase over nadir for the reappearing lesion. Otherwise, the response is CR.
- If the previous target lesion response was PR, then the response should be evaluated based on the SOD.

Notes:

The SOD is only considered if the methods of assessment are consistent with baseline. The “interchangeable” methods noted in [Section 10.1.1](#) above are all considered consistent methods.

In the SOD, the longest diameter will be used for non-nodal lesions and the short axis dimension will be used for each lymph node included in the sum.

10.2.2. Response Evaluation of Non-Target Lesions

- CR is defined by the complete disappearance of all non-target lesions (where all non-target lesions are marked “Absent” on the “Non-Target Lesion” eCRF). All lymph nodes must be non-pathological in size (< 10 mm in short axis).
- Non-CR/Non-PD is defined by persistence of one or more non-target lesions (ie, if any non-target lesions are marked “Present” on the “Non-Target Lesion” eCRF).
- NB is assigned if “No Non-Target Lesions” is marked on the “Lesion Assessment Y/N” eCRF at baseline.
- NAE is assigned if, in the absence of PD based on evaluated non-target lesions:
 - Any individual non-target lesion is evaluated as “Not Evaluable” (marked as “Not Evaluable” on the “Non-Target Lesions” eCRF).
 - Inconsistent methods (unless considered “interchangeable” as noted in [Section 1.2](#)) are used for any non-target lesions after start date.
 - One or more non-target lesions are not assessed.

- PD is assigned if any non-target lesion is marked “unequivocal progression” on the “Non-Target Lesion” eCRF.
 - Note: the lesions assessed are only considered for CR, Non-CR/Non-PD and PD if the methods of assessments are consistent with baseline. The “interchangeable” methods noted in [Section 10.1.1](#) above are all considered consistent methods.

10.2.3. New Lesion Evaluation Criteria

A new lesion is defined by the appearance of 1 or more new lesions on the “New Lesions” eCRF.

Any lesion that is recorded for the first time after the start date without being marked on the “New Lesions” eCRF must be queried. In case the inconsistency is not resolved at time of database snapshot/lock, the lesion will be considered as new and the participant in progression at that time point.

The requirement for consistent methods of assessment with baseline does not apply for new lesions.

